7.3 Table 1. Study Measures and Time Points

Table 1. Measures		Bio-behavioral Laboratory Visits		
Description of Time Point	Visit 1	Visit 2	Visit 3	
Demographic & Baseline Covariates				
Demographics	X			
Tobacco History	X			
Nicotine Dependence	X			
CO	X	X	X	
Urine Cotinine	X	X	X	
Predictor Variables				
Risk Perceptions	X			
Sensation Seeking	X			
Depression	X			
Cigarillo Advertising & Marketing Exposure	X			
Marijuana & Alcohol use	X	X	X	
Tobacco use	X	X	X	
Outcome Variables				
Subjective rewarding value of cigarillo flavoring	X			
Relative reinforcing value of cigarillo flavoring		X		
Absolute reinforcing value of cigarillo flavoring				X

CONFIDENTIAL

This material is the property of the University of Pennsylvania. Do not disclose or use except as authorized in writing by the study sponsor

7.4 Description of Study Measures

7.4.1 Screening

Urine Drug Screen: A urine sample (~30ml) will be collected at Laboratory Visit 1 to conduct a urine drug screen. The urine drug screen indicates whether the subject has recently taken any of the following recreational drugs or medications: THC, cocaine, opiates, amphetamines, methamphetamines, phencyclidine (PCP), ecstasy (MDMA), barbiturates, benzodiazepines, methadone, tricyclic antidepressants, and/or oxycodone. Participants with a positive urine drug screen for any substance listed above other than THC and (prescribed) amphetamines and/or tricyclic antidepressants will be deemed ineligible. A urine sample that doesn't register a temperature reading of at least 90 degrees Fahrenheit will not be considered a valid sample. In an effort to remain CLIA-compliant, results from urine drug screen will not be shared with participants. Participants will be informed that the testing is for research purposes only and that they will be informed of their eligibility status, but not of the specific testing results. In order to document inclusion/exclusion criteria for regulatory purposes, results of the urine drug screens (test cup) will be retained in research charts and in an electronic research record within our local data management system (Access). These results are not and will not be entered into a participant's electronic medical record.

Urine Pregnancy Test: At Laboratory Visit 1, female participants will be supplied with a simple, CLIA-waived hCG pregnancy test strip and a urine sample cup. Female participants will be informed that pregnant women are not advised to participate in this research study. Participants will then be instructed to self-administer the pregnancy test and inform the study staff if they would like to continue participation after they have reviewed the results of the pregnancy test. Participants will be informed that there is no penalty for discontinuing participation at this point in the visit and that they will still receive travel reimbursement for the visit.

Breath Alcohol Concentration (BrAC): Participants will complete a BrAC assessment at Laboratory Visit 1. Participants will be made aware of the BrAC assessment prior to the visit and asked to avoid alcohol and alcohol-based products (e.g. mouthwash, breath spray, etc.) the evening and morning before Laboratory Visit 1. The BrAC monitor is a handheld device that uses a disposable mouthpiece and reports the concentration of alcohol in exhaled breath. Any reading greater than 0.000 indicates alcohol consumption within the last 14 hours. Participants with a BrAC greater than 0.000 at Laboratory Visit 1 will be deemed ineligible.

Medical History Form: A medical history form (led by the research staff) will be completed to review for applicable contraindications previously listed under Key Inclusion/Exclusion Criteria at Laboratory Visit 1.

Demographics and Smoking History: Standard surveys will collect demographics information such as age, sex, race, ethnicity, education level, and income. Standard survey questions will assess cigarillo use history (number and flavored), use of other combustible products, as well as cigarette smoking history (e.g., age at initiation, current smoking rate). Nicotine dependence will be assessed with the Fagerstrom Test for Nicotine Dependence (FTND). This 6-item measure has good internal consistency ($\alpha = .64$) and high test-retest reliability. Nicotine dependence will also be assessed using the Hooked on Nicotine Checklist (HONC).

Adverse Events Form (Open-Ended AEs): Participants will be asked an open-ended question about any symptom or medical event that may be related to their study participation. These events will be documented as **unanticipated (unexpected) AEs** unless they are otherwise outlined in the protocol and/or consent form (i.e. related to withdrawal, assessments, etc.). The reporting period for each assessment will inquire about any event(s) or symptom(s) experienced since the last in-person visit. If a participant reports a symptom or medical event, they will be asked to rate the severity of the

CONFIDENTIAL

This material is the property of the University of Pennsylvania. Do not disclose or use except as authorized in writing by the study sponsor

event utilizing the following severity scale: 0 (None=No Concerns), 1 (Mild=Issue does not interfere with usual daily activities), 2 (Moderate=Issue does interfere with some activities), and 3 (Severe=No normal activities are possible). See section 8.2.1: AE Collection Methods for further details.

Carbon Monoxide (CO) will be measured using a Vitalograph CO monitor (Lenexa, KS). A CO > 5 is indicative of combustible cigarette smoking. At the start of visits 2 and 3, 10-hour tobacco abstinence will be assessed via CO < 10 or 50% of the CO value measured at Visit 1.

Urine Cotinine will be measured using a test strip kit that detects the presence of cotinine in a urine sample along three detection levels: low, medium, and high. The testing kit indicates the presence and amount of cotinine measured in the urine, which is a product of nicotine metabolism with sensitivities of 50 ng/mL (low concentration), 200 ng/mL (medium concentration), and 600 ng/mL (high concentration). Participants will provide a urine sample for cotinine analysis with the expectation that cotinine level will be at least one tier lower than cotinine level at Visit 1; participants already measuring in the lowest tier are expected to remain there.

Concomitant Medications: At Laboratory Visit 1, participants will be asked to list all medications (prescription or non-prescription) and NRTs currently taken and/or recently discontinued (within the past 14 days) as a baseline collection. All information will be collected on a Concomitant Medication Log that will be maintained within the participant's study chart. At every subsequent in-person visit, participants will be asked if they have taken any additional medications (prescription or non-prescription), NRTs, and/or changed the dosage or stopped taking any previously reported medications since their last in-person visit. Participants who report taking contraindicated medication(s) over the course of the study period may only remain eligible if the Principal Investigator determine that the contraindicated medication(s) did not impact the study design, data quality, and/or participant safety and welfare.

7.4.2 Covariates – All Measured at Laboratory Visit 1

Demographics. Sex, age, education and employment will be measured at baseline. Available research suggests that women are more likely than men to use flavored cigarillos [8]. Cigarillo use history (number, flavor preference) will be included in the statistical models.

Risk perceptions of flavored cigarillo use (e.g., impact of flavor on risk and addictiveness) will be measured with six Likert-style items derived from previous and ongoing research (0=not at all to 6=extremely). The Center for Epidemiologic Studies **Depression** Scale (CES-D) is a 20-item Likert- style measure with high internal consistency ($\alpha > .85$), and correlates with clinical ratings of depression severity. The CES-D has been used in adolescent and young adult tobacco studies. Young adults who use cigars such as cigarillos report higher levels of depression symptoms compared to those who do not use cigarillos. Flavoring appears to enhance the mood of young adults who use cigarillos. As such, we will not screen out for elevated depression symptoms. We will measure them and include them as a covariate in the statistical models as depression symptoms may underlie flavor preference. **Sensation seeking** will be measured with the 8-item Brief Sensation Seeking Scale (1=strongly disagree to 5=strongly agree) given its associations with little cigar and cigarillo use [47,100,150,151]. **Exposure to flavor-related advertising and marketing practices** will be measured with 9 items adapted from PATH and previous research. These items evaluate the source (e.g., Internet, social media, retail stores) and type (e.g., giveaways, direct mail and e-mail coupons, links to on-line vendors, branded merchandise, celebrity endorsement, music event sponsorship) of exposure to flavored cigarillo promotions.

Standard epidemiological items will measure lifetime and current use (monthly, weekly, daily, and rate) of **other tobacco products** such as combustible cigarettes (including menthol status), e-cigarettes, large and little cigars, and hookah. Lifetime and current use of **marijuana** (combustible, vaporized, and edible) will be assessed via items used in previous research and surveillance studies. Use of cigarillos for blunts will be measured and differentiated from cigarillo tobacco use

CONFIDENTIAL

This material is the property of the University of Pennsylvania. Do not disclose or use except as authorized in writing by the study sponsor

as intended. **Alcohol use** will be measured with epidemiological questions of lifetime, past 30 day use, as well as binge drinking episodes.

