5 CHARACTERISTICS OF THE STUDY POPULATION

5.1 *Target Population*

Participants will be 86 male and female young adults (ages 18-24 years old) who have used \geq 10 cigarillos in their lifetime.

We chose \geq 10 cigarillos/lifetime as a minimum criterion for participation to ensure that cigarillo exposure during the course of the study does not exceed lifetime exposure. As such, completely naïve young adults will not be exposed to cigarillos and regular cigarillo users with well-developed biases in favor of flavored cigarillos will not be included. We will measure cigarillo use history (flavor, non-flavored) and flavor preferences at baseline.

5.2 *Accrual*

We propose to recruit 100 young adults to ensure 86 participants with complete data at study end. Young adults will be recruited from the community through Internet-based advertisements (e.g., Craigslist, social media) and print advertisements including publications at 2-year and 4-year universities. Young adults who respond to the ads will be prescreened for inclusion and exclusion criteria over the telephone. In order to determine whether the ad respondents meet the inclusion criteria for lifetime cigarillo use, use of cigarillos and other tobacco products (e.g., large and little cigars) will be measured and differentiated through product description, and brand examples of the most popular brands of each product will be provided to aid accurate reporting. Research indicates that the inclusion of brand information increases self-reported cigar use. We will assess whether cigarillos and other cigar products are used as intended or modified for blunting. Cigar products modified for blunting will not count toward the inclusion cutoff for cigar exposure. The number of cigarillo blunts used in the past month and the brand characteristics (untipped, flavor) will be recorded at baseline.

Those meeting initial criteria will be screened at the beginning of Laboratory Visit 1 at the Bio-Behavioral Laboratory (BBL). After providing written informed consent, potential participants will provide a urine sample for a drug screen and a pregnancy test (females only) to determine final eligibility.

CONFIDENTIAL

This material is the property of the University of Pennsylvania. Do not disclose or use except as authorized in writing by the study sponsor

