5.4 Exclusion Criteria

Subjects who present and/or self-report with the following criteria will not be eligible to participate in the study:

Smoking Behavior

1. Use of less than 10 cigarillos in lifetime.
2. Current enrollment or plans to enroll in a tobacco cessation program over the duration of the study.
3. Current use of nicotine replacement therapy or other smoking cessation medication.

Alcohol and Drug

1. History of substance abuse (other than nicotine dependence) in the past 12 months and/or currently receiving medical treatment for substance abuse. Counseling and support groups (e.g., Alcoholics Anonymous and Narcotics Anonymous) will not be considered medical treatment for the purposes of this protocol.
2. Current alcohol consumption that exceeds 25 standard drinks/week.
3. Breath alcohol reading (BrAC) greater than .000 at Laboratory Visit 1.
4. Use of e-cigarettes on > 15 days in the past 30 days.

Medical

1. Women, including all individuals assigned as “female” at birth, who are pregnant, breast feeding, or planning a pregnancy over the duration of the study period.
2. Serious or unstable disease within the past year (e.g., cancer, heart disease). Applicable conditions will be evaluated on a case-by-case basis by the Principal Investigator.

Psychiatric

1. Lifetime history of schizophrenia or psychosis.
2. Lifetime history of suicide attempt(s) requiring intervention AND recurring suicidal thoughts or ideations. Evaluated on a case-by-case basis by the Principal Investigator.
3. Current or recent use of anti-psychotic medications.

General Exclusion

1. Past, current, anticipated, or pending enrollment in another research program over the study period that could potentially impact subject safety, study data, and/or the study design as determined by the Principal Investigator.
2. Any medical condition, illness, disorder, adverse event (AE), or concomitant medication that could compromise participant safety or significantly impact study performance as determined by the Principal Investigator. Subjects may be deemed ineligible for any of

CONFIDENTIAL

This material is the property of the University of Pennsylvania. Do not disclose or use except as authorized in writing by the study sponsor

the aforementioned reasons at any point throughout the study, as well as during the initial telephone screen.

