3. Complete a UDS (at least 30ml [two tablespoons] of urine). The UDS will assess the use of any study-prohibited medications/recreational drugs (See Key Exclusionary Criteria; Alcohol and Drug). Participants who test positive for any exclusionary medications or recreational drugs per this protocol will be deemed ineligible.
 - a. The UDS sample will also be used for urine cotinine analysis.
4. Female participants only: Self-administer a CLIA-waived urine pregnancy test. Female participants are advised that participation of pregnant women in this study is prohibited and that they may withdraw at any time.
5. Perform a BrAC assessment to control for alcohol consumption. Participants with a BrAC greater than 0.000 at Laboratory Visit 1 will be ineligible.
6. Perform a CO breath assessment and collect self-report smoking behavior over the past 24 hours to control for prior tobacco exposure.
7. Answer questions about use of marijuana, other tobacco products (besides cigarettes), or vaping of any substance including tobacco/nicotine or other drugs in the past month.
8. Complete measures of Demographics, Smoking History (e.g., duration, rate, regular and/or menthol), FTND (Fagerstrom Test of Nicotine Dependence), and HONC (Hooked on Nicotine Checklist)
9. Complete a Medical History Form with a member of the research team to review for applicable contraindications, including psychiatric exclusions, previously listed under Inclusion and Exclusion Criteria (section 4.3 and 4.4).
10. Complete a baseline concomitant medication review (if applicable).
11. Complete questionnaires:
 - a. Adverse Events Form (Open-Ended AEs)
 - b. Depression, sensation-seeking, risk beliefs, cigarillo advertising and marketing exposure
12. Use study-provided cigarillos during a session in our smoking lab (required). During this smoking task, participants will sample two puffs from each of three cigarillos. Sampling of each cigarillo will be separated by 20 minutes and the order will be counterbalanced.
13. Be reminded to engage in tobacco abstinence (e.g., combustible cigarettes, e-cigarettes, cigars, blunts) and combustible marijuana abstinence for 10 hours in preparation for Laboratory Visit 2.
14. Tentatively schedule next study visit with a member of the research team.

7.2.3 Laboratory Visit 2

During Laboratory Visit 2, (Duration: ~ 2 hours) participants will:

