Reproductive Risks: Smoking can cause serious harm to unborn children or children who are breast-feeding. Female participants are asked to use a medically accepted method of birth control (such as IUD, birth control pills, condoms, etc.) while participating in the study. Further, female participants, and those assigned as female at birth, will be asked to administer a simple, one-step hCG pregnancy test and informed that if they are (or believe they may be) pregnant that they will not be eligible to participate in the research study. If a female participant becomes pregnant over the course of the trial, they will be immediately withdrawn. It will also be recommended that the participant seek consult from an obstetrician or maternal-fetal specialist about the dangers of smoking while pregnant.

Assessments: Some participants may experience some emotional distress during the assessments due to learning their carbon monoxide levels or seeing how many cigarillos they smoke. These events happen very rarely and in almost all cases are short-lived and of low intensity. If a participant does exhibit a high level of emotional distress, however, they will be offered contact information for mental health services in the area.

CONFIDENTIAL

This material is the property of the University of Pennsylvania. Do not disclose or use except as authorized in writing by the study sponsor

Email Communications: In this research study participants may prefer to receive appointment reminders via email or submit questions related participation via email. Email is not a secure means of communication. Email messages travel across the Internet passing through multiple computers before reaching their final destination. It is not possible to know whether an email a participant sends will be viewed along the way. Additionally, if sent messages are not deleted, an email provider may have an archive of everything that is sent. If someone gets access to an email account (for example, a participant's family member), they could see archived messages. There are many other ways in which emails are not secure—these are only selected examples. To manage this risk the informed consent form will include specific language to educate research participants on the privacy risks involved in email communications. Participants will also be explicitly instructed to only use email communications for routine matters and never for personal or confidential messages or questions.

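### Section 7.4.1 leaves continuation after the pregnancy test to the participant, although pregnancy is an exclusion, and no section gives staff the result before the first puffs

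*Combined protocol and SAP*

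**What the plan says.** Four sections treat pregnancy as disqualifying.

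- Section 5.4 excludes women "who are pregnant, breast feeding, or planning a pregnancy over the duration of the study period".
- Section 5.2 says that candidates "will provide a urine sample for a drug screen and a pregnancy test (females only) to determine final eligibility".
- Section 8.1 (Reproductive Risks) has women "informed that if they are (or believe they may be) pregnant that they will not be eligible to participate in the research study", and withdraws at once anyone who becomes pregnant during the trial.
- Section 8.3.1 names pregnancy as an exclusion that the urine sample is collected to assess.

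Two sections describe how the test is run. Section 7.2.2 item 4 has the woman administer it herself and advises her that "participation of pregnant women in this study is prohibited". Section 7.4.1 (Urine Pregnancy Test) instead tells her that "pregnant women are not advised to participate in this research study", and asks her to "inform the study staff if they would like to continue participation after they have reviewed the results of the pregnancy test". It adds that there is no penalty for stopping and that travel is still reimbursed.

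The neighbouring checks are firmer. For breath alcohol, 7.2.2 item 5 states: "Participants with a BrAC greater than 0.000 at Laboratory Visit 1 will be ineligible". For the drug screen, 7.4.1 makes a disqualifying result a ground for ineligibility and says that "results of the urine drug screens (test cup) will be retained in research charts and in an electronic research record".

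**The concern.** Section 7.4.1 puts the exclusion into practice, and it is the one section that does not state it as an exclusion. It describes advice followed by a choice. The only thing passed to staff is whether the participant wants to go on. Staff working from 7.4.1 and staff working from 5.4 would have different instructions at the same step.

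What is at stake is participant safety and the eligibility record. Section 8.1 itself describes smoking as a cause of serious harm to an unborn child, and this exclusion is the protection at entry. If the result is neither seen nor recorded, the file need not show that the exclusion was applied.

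The payment schedule also makes a stated wish to continue a weak control. A woman who stops at the test is promised travel reimbursement, which is \$5 for Visit 1 in Table 2. Completing Visit 1 pays \$55 including travel, and completing the study pays up to \$240.

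**Working it through.** The protocol gives no figure on this point to reproduce. The check compares the three Visit 1 screens and then asks whether any other step could catch a positive pregnancy test before the first puffs.

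**The three screens compared (7.2.2 items 3 to 5, and 7.4.1)**

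| | Drug screen | Breath alcohol | Pregnancy test |
|---|---|---|---|
| Who carries it out | Participant gives urine; results are not shared with her | Participant performs the breath test at the visit | Participant administers and reviews it herself |
| Adverse result stated to mean ineligible in the procedure text | Yes, with listed exceptions | Yes, any reading above 0.000 | No; item 4 states a prohibition but ties no action to the result, and 7.4.1 offers a choice |
| Result stated to be kept | Yes, chart and database | Not stated | Not stated |
| What staff are said to receive | The result | Not spelled out, but an ineligibility rule is attached | Her wish to continue |

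**Other steps that could catch it, against the first exposure at 7.2.2 item 12**

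1. *Medical History Form (7.2.2 item 9).* Staff-led, and before item 12. It reviews contraindications in general terms, and the test result is not said to feed into it.
2. *Real-time review of eligibility data (11.3.2 and 11.4).* Takes place at Visit 1. It can act only on data that staff hold, and 7.4.1 does not give them the result.
3. *Final Eligibility Checklist (11.3.3).* Completed after Visit 1, so after the Visit 1 puffs. It could still act before Visit 2.
4. *Data-system eligibility check at randomization (10.3).* Also placed after Visit 1.

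Steps 1 and 2 come early enough but are not linked to the result. Steps 3 and 4 come too late for the first exposure.

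**Exposure if a woman with a positive test continues**

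- Visit 1: 3 cigarillos × 2 puffs = 6 puffs (7.2.2 item 12).
- Visit 2: 10 puffs (6.2 and 8.1).
- Fixed total: 6 + 10 = 16 puffs.
- Visit 3: a 90-minute ad libitum session, typically 0 to 2 cigarillos (6.2).

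If the later checklist stops her before Visit 2, the exposure is the 6 puffs of Visit 1. If nothing stops her, it is 16 fixed puffs plus whatever she smokes at Visit 3.

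**The case against.** The strongest reply is that the governing rule is plain. Eligibility is set by 5.4, and 5.2, 7.2.2, 8.1 and 8.3.1 agree with it. One loosely worded sentence in a description of measures should not override them, and 7.4.1 nowhere says that a pregnant woman may continue. It is true that the weak wording is confined to 7.4.1, and that staff who know 5.4 would probably exclude a woman who disclosed a positive test. But the rule has to be applied to a result, and the procedure does not put that result in staff hands.

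Second, the staff-led medical history comes before the first puffs, and a review against the criteria need not name each criterion to cover it. This has some force. As written, though, that review would rest on what the woman chooses to report, not on the test.

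Third, the Manual of Procedures, case report forms, checklist and consent form are not among the documents, and a field for the result may exist in one of them. That cannot be excluded. The point is therefore that the protocol does not require the result to be recorded, not that it goes unrecorded.

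Fourth, self-testing may be a deliberate privacy choice, and the drug-screen comparison is imperfect because those results are withheld from participants, so staff have to handle them. This is fair, and the fix keeps the test self-administered.

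Finally, the full exposure requires a positive test, a wish to continue despite being told elsewhere that participation is prohibited, and failure of the later checklist. The 16-puff figure is a conditional worst case.

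**Conclusion.** The concern holds. Section 7.4.1 conflicts with 5.2, 5.4, 7.2.2 item 4, 8.1 and 8.3.1, and no section provides for staff to see or record the pregnancy result before the first cigarillo exposure. The procedure as stated could let a woman with a positive test proceed to smoke.

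The size depends on events for which the documents give no rate: a positive test at Visit 1 followed by a wish to continue. Given those, and assuming the medical history and real-time review do not bring out the result, exposure is at least the 6 puffs of Visit 1, and up to 16 fixed puffs plus the ad libitum session if the later checks also miss it. Sample size, power and the primary analyses are unaffected. This should be corrected because it concerns a protection the protocol itself relies on and the correction is cheap.

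**What to change.** - In 7.4.1, replace the advisory wording with a statement that pregnant women are not eligible.
- In both 7.4.1 and 7.2.2 item 4, state that a positive result makes the participant ineligible, in the same form as the breath alcohol rule in item 5.
- Keep the test self-administered, but have the participant show the strip to a staff member. If that is judged too intrusive, a recorded self-report of a negative result is a less secure alternative.
- Record the result in the Visit 1 eligibility data before item 12. The Final Eligibility Checklist can confirm it afterwards but should not be the only record.
- Keep the existing assurance of no penalty and reimbursed travel.

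The cost is wording in two sections and one field in the Visit 1 eligibility data; the test is already performed. Staff would learn the pregnancy result, a small loss of privacy, so it should be handled with the same confidentiality as the drug-screen results. Whether the consent form needs matching wording cannot be judged from these documents.
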